# 7. STUDY OPERATIONS

## 7.1. **Protocol Deviations**

A protocol deviation is any noncompliance with the clinical trial protocol or International Council for Harmonization of Technical Requirements for Pharmaceuticals for Human Use Good Clinical Practice requirements. The noncompliance may be either on the part of the participant, the investigator, or the study site staff. Protocol deviations will be recorded on the source documents and with an explanation for the deviation. All protocol deviations will also be recorded as specified in the monitoring plan.

Protocol deviations will be identified by site staff, through medical reviews, and by clinical research associates during site monitoring. A data review will be conducted before database lock by the sponsor to classify protocol deviations as minor or major. Deviations that may alter or confound interpretation of the study results will be classified as major deviations. Protocol deviations will be summarized as counts and percentages by treatment group and overall, deviation severity, and category for all randomized patients. Patients will be counted once for each category within each level of severity. Deviations will also be presented by patient in a data listing for all randomized patients.

# 7.2. Randomization

Approximately 440 patients are planned to be randomized in the study. Patients will be randomized in a 1:2:1 ratio (12 mg BID:8 mg BID:placebo) to each of three study arms:

- CTP-543 12 mg BID
- CTP-543 8 mg BID
- Placebo BID

Randomization will be stratified by scalp hair loss into one of the following two categories: 1) Partial scalp hair loss (SALT  $\geq$  50 and < 95); 2) Complete or near-complete scalp hair loss (SALT  $\geq$  95). The randomization schedule will be generated prior to study start.

All study patients, Investigators, and site study staff will be blinded to study drug assignment for the duration of the study. Tablets and packaging of CTP-543 and placebo will be identical in appearance.

A by-patient listing of randomized treatment group and randomization number will be presented.

# 7.3. Measures of Treatment Compliance

Patients will strive for 100% compliance with the daily dosing schedule. Treatment compliance will be summarized as percent of planned dose received for each dosing regimen. Percent of planned dose received will be calculated for the entire treatment period as follows:

100\*(Tablets Dispensed-Tablets Returned)/(Tablets Expected)

Tablets Expected is defined as the time on treatment multiplied by the expected number of pills taken daily (x2 for the 12 mg BID group; x2 for the 8 mg BID group; x2 for the placebo group), where time on treatment is defined as treatment end date – treatment start date + 1. Dose

interruptions will be ignored in this calculation. Derived patient compliance, compliance per the eCRF (80% or higher versus less than 80%), and dosing exceptions will be listed in by-patient data listings.

For patients who roll over into one of the open label extension studies, it will be assumed that only 1 dose of study drug was administered for the last dose of study drug. For patients who do not roll over, it will be assumed that 2 doses of study drug were administered for the last dose of study drug.

#### 8. **ENDPOINT EVALUATION**

#### 8.1. **Overview of Efficacy Analysis Methods**

#### 8.1.1. **Multicenter Studies**

Patients will be enrolled at up to 60 sites; site identifiers will be included on by-patient listings.

#### 8.1.2. **Assessment Time Windows**

The visit schedule for all study assessments is provided in Appendix 15.2. Patients will be considered completed for efficacy analyses after Week 24 (Visit 9). Patients will either complete treatment at Week 24 and have a safety follow-up visit at Week 28 (Visit 10) prior to exiting the study, or if eligible, may enroll into an open-label extension study of CTP-543 at their Week 24 visit.

Unscheduled visits and early termination visits will be reassigned based on the analysis windows in the below table and the schedule of events. Assessments may only be re-assigned to visits where they were to be collected per the schedule of events. The latest assessment in a window will be selected as the visit used in summaries, unless otherwise specified. All visits will be included in by-patient data listings.

	Safety Analyses				Efficacy Analyses			
Nominal Visit	Lower	Lower Target Upper		Lower	Target	Upper		
Screening	-28	-1	-1	-28	-1	-1		
Visit 2-Day 1	1	1	1	1	1	1		
Visit 3-Week 2	2	15	22	12	15	18		
Visit 4-Week 4	23	29	43	26	29	32		
Visit 5-Week 8	44	57	71	54	57	60		
Visit 6-Week 12	72	85	99	82	85	88		
Visit 7-Week 16	100	113	127	110	113	116		
Visit 8-Week 20	128	141	155	138	141	144		
Visit 9-Week 24	156	169	183	166	169	172		
Visit 10-Week 28	184	197	211	194	197	200		

Table 2: Analysis Windows for Unscheduled and Early Termination Visits

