## 8.3. Patient Withdrawal Criteria

For all patients, it is the intent that patients who discontinue study medication (at any time) for any reason will continue to be followed for all protocol-planned study visits through the completion of the 24-week treatment period, and will have all endpoints (including efficacy) collected accordingly.

The Investigator, Sponsor, or its designee may decide a patient should discontinue treatment at any time and for any reason. In addition, patients will discontinue randomized treatment if they:

- Experience an intolerable adverse event: such events include, but are not limited to, adverse events ≥ Grade 4\*, bone marrow-related events, a ≥ Grade 3\* cardiac event (\*CTCAE v5.0 criteria);
- Require a medication that is prohibited by the protocol. However, under certain circumstances, and in consultation with the Medical Monitor, short-term use of a prohibited medication may not necessitate withdrawal of treatment when its use is unlikely to unfavorably alter the risk-benefit of subject participation;
- In the opinion of the Investigator, have any medically appropriate reason;
- Become pregnant;
- Have a serious adverse event associated with a SARS-CoV-2 infection;
- The Investigator believes that further treatment is undesirable or the risk-benefit profile has become unfavorable.

Furthermore, dose interruptions lasting more than 21 days may require treatment discontinuation on a case by case basis following consultation with the Medical Monitor.

In addition, patients are free to withdraw from participation in the study at any time, for any reason, and without prejudice. The Investigator must withdraw any patient from the study if the patient withdraws consent and requests to stop participating in the study. Patients who withdraw or are withdrawn from the study will not be replaced.

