## 9.2.1. Dose Interruption Safety Criteria and Management

Patients who experience hematologic adverse events as described in Table 3, significant clinical laboratory abnormality, or adverse events that may reflect an unfavorable risk-benefit profile may have their dose interrupted at the discretion of the Investigator. The Medical Monitor(s) should be consulted whenever possible prior to decisions for dose interruption.

Patients who withdraw consent and therefore are discontinued from the study should undergo an Early Termination Visit and subsequent Safety Follow-up Visit as appropriate per Section 8.3.1 Patient Withdrawal Procedures, and associated adverse events followed as described in Section 11 Adverse Events.

Hematology parameters will be assessed bi-weekly for the first 4 weeks of the Treatment Period, and every 4 weeks thereafter for the remainder of the study. Prior to dose interruption, hematology parameters should be confirmed with repeat testing at an Unscheduled Visit within 72 hours, except in severe cases (i.e.: neutrophil counts below 0.5 x 10^9/L) where immediate interruption of dosing is necessary for the safety of the patient. **Blood draws confirming dose interruption criteria should occur prior to the first daily dose on the day of draw.** 

Dose interruption requirements for hematologic abnormalities are provided below. However, less significant changes may warrant clinical intervention and the Investigator should use his/her best clinical judgment when considering a dose interruption whether for singular or aggregate hematology results above the limits provided in Table 3, or for other clinical signs, symptoms, or considerations that suggest dose interruption is in the best interest of the patient.

Table 3: Selected Hematologic Thresholds for Dose Interruption

| Neutrophil Count                             | Dose Adjustment  |
|--|--|
| Between 0.5 to 1 x 10  /L        | Interrupt dose until recovered to greater than 1.5 x 10  /L and  |
| (Grade 3)                                    | resume dosing at previous dose   |
| Less than 0.5 x 10  /L (Grade 4) | Severe case: Interrupt dose immediately and repeat CBC with differential within 72 hours. Recommend hematology consult and contact medical monitor. Permanent discontinuation of treatment should occur upon repeat confirmation of value |
| Female Hemoglobin Level                      | Dose Adjustment  |

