#### 10.14. Unscheduled Visit

In addition to regularly scheduled protocol visits, an Unscheduled Visit may be conducted to ensure appropriate safety monitoring or follow-up of the patient, at the discretion of the Investigator. For example, an Unscheduled Visit may be scheduled to monitor potential or actual clinically meaningful safety laboratory results, for confirming hematology results to support dose interruption or resumption of dosing thereafter, for suspicion of tuberculosis, or for other clinical signs, symptoms, or considerations that warrant additional safety follow-up. Only those criteria requiring additional monitoring should be performed at an Unscheduled Visit. An Unscheduled Visit will not replace regularly scheduled protocol visits.

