#### Sensitivity 1: Multiple imputation; missing not at random (MNAR)

This sensitivity analysis is an implementation of a pattern mixture model that draws from different populations based on the reason for withdrawal from study. Patients who discontinued the study early due to a treatment-emergent adverse event (including COVID-19) or due to lack of efficacy will be considered MNAR. Treatment-emergent adverse event and lack of efficacy are reasons collected under "If 'Withdrew Consent', specify reason" on the *Study Discontinuation/Completion* eCRF page.

For patients who discontinued the study early due to a treatment-emergent adverse event or lack of efficacy, SALT scores missing after discontinuation will be imputed using the control arm. This assumes that patients, regardless of treatment, who discontinue the study early for those reasons would have similar SALT scores to placebo patients with complete data.

For patients who discontinued the study due to reasons other than treatment-emergent adverse event or lack of efficacy, missing SALT scores after subjects discontinue the study early will be multiply imputed from subjects within the same treatment group who have complete data at that time. Terms will include baseline values and the weekly data through the time point being imputed.

The proportion of patients who have a SALT score  $\leq 20$  will be calculated for each imputed dataset. The primary analysis, as described in Section 8.2.2, will be repeated for the Efficacy Population using the MI with MNAR assumption datasets.

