#### 8.5. Other Endpoints

A KM plot of time to first instance of post-baseline SALT  $\leq 20$  will also be included. Patients who do not meet the responder criteria will be censored at treatment end date or 24 weeks if the treatment end date extends beyond 24 weeks. Stratified log-rank statistics will be computed by randomization strata for CTP-543 8mg v. placebo and CTP-543 12mg v. placebo separately. The p values will be displayed with the KM plot. These p values are descriptive and are not part of the hierarchy outlined in Section 8.1.4 (Figure 1).

No other efficacy endpoints are specified.

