# **15. APPENDIX**

# **15.1.** Study Flow Chart

# 15.2. Schedule of Events

	Screening	Baseline/ Randomization	Treatment Period 				Safety Follow-Up
Event 	Day -28 to Day -1  (Visit 1)	Day 1  (Visit 2)	Week 2 (Visit 3)	Week 4, 8, 12 (Visit 4, 5, 6)	Week 16, 20 (Visit 7, 8)	Week 24 (Visit 9)/ ET Visit	Week 28 (Visit 10) 
Informed consent	Х						
Eligibility assessment	Х	Х					
Demographics	Х						
Medical history	Х	Х					
Randomization		Х					
Complete physical examination	Х	Х				Х	X
Brief physical examination				X	Х		
Height	Х						
Weight	Х	Х		X	Х	Х	X
Pregnancy test 	Х	Х		Х	Х	Х	Х
Tuberculosis test	Х						
Clinical laboratory testing 	X 	Х	$X^{10}$	Х	Х	Х	Х
Pharmacokinetic Sampling for Population Pharmacokinetics		Х		X 		Х	
HBV and HCV test	Х						
12-lead electrocardiogram	Х			X 		Х	
Vital signs	Х	Х		Х	Х	Х	Х
Severity of Alopecia Tool assessment 	Х	Х		Х	Х	Х	
Photographs of the scalp	Х	Х		Х	Х	Х	
Photographs of eyebrows, eyelashes, and hands		Х		X 		Х	
Eyebrow Assessment (BETA)		Х		X 		Х	
Eyelash Assessment (BELA)		Х		X 		Х	
Patient Reported Outcome Scales: SPRO and QPRO		Х		X 	Х	Х	
Patient and Clinical Global Impression of Improvement (PGI-I, CGI-I  )				X 	Х	Х	
Patient and Clinical Global Impression of Severity (PGI-S, CGI-S  )		Х		X 	Х	Х	
Hospital Anxiety and Depression Scale (HADS)		Х				Х	
Dispense study drug 		X		X	X		
Study drug accountability				X	Х	Х	
Adverse events 	Х	X	Х	X	X	Х	X
Concomitant medications 	Х	Х	Х	X	Х	X	Х

HBV = hepatitis B virus; HCV = hepatitis C virus	 For females of childbearing potential, a serum pregnancy test will be performed at
 Due to the COVID-19 pandemic, patient study visits may be performed remotely when	Screening. Throughout the Treatment Period, and at the safety follow-up (if applicable) urine pregnancy tests will be performed
should strive to perform assessments per the schedule of events above with the	 Includes fasted hematology, serum chemistry, and lipids performed by the central
understanding that all assessments may not be able to be performed (ECGs, vitals, SALT	lab.
assessments).	o Collected pre-dose.

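### Does an early-termination SALT score that falls in no efficacy window risk being counted as an observed Week 24 result?

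*SAP*

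**What the plan says.** SAP 8.1.2 sends off-schedule visits through a set of windows: "Unscheduled visits and early termination visits will be reassigned based on the analysis windows in the below table and the schedule of events". It then limits where an assessment may go: "Assessments may only be re-assigned to visits where they were to be collected per the schedule of events". Table 2 has two sets of windows. The safety windows are contiguous. The efficacy windows are seven days wide with gaps between them, and Week 24 efficacy is Days 166-172. All visits are to appear in listings.

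The schedule (SAP Appendix 15.2, as in Protocol Table 2) marks SALT in a column headed "Week 24 (Visit 9)/ ET Visit". Its footnotes date every visit from Day 1 and allow ±2 days.

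SAP 8.2.1 multiply imputes missing post-baseline SALT scores within arm. For patients who leave the study because of a treatment-emergent adverse event or lack of efficacy, Sensitivity 1 in SAP 8.2.3 says "SALT scores missing after discontinuation will be imputed using the control arm". SAP 8.5 adds a descriptive Kaplan-Meier plot of "time to first instance of post-baseline SALT" ≤20.

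Protocol 8.3 intends that "patients who discontinue study medication (at any time) for any reason will continue to be followed for all protocol-planned study visits". Under Protocol 9.2.1, those who withdraw consent "should undergo an Early Termination Visit and subsequent Safety Follow-up Visit as appropriate". Protocol 10.14 keeps unscheduled visits narrow: "Only those criteria requiring additional monitoring should be performed at an Unscheduled Visit".

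**The concern.** A patient who withdraws can have the ET visit on any day, and most days before Week 24 lie outside every SALT efficacy window. The SAP does not say what happens to a score on such a day. There are two candidate readings:

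- **Unassigned.** The score belongs to no visit, and Week 24 is imputed.
- **Observed Week 24.** No window claims the score, so it stays in its schedule column, which is shared with Visit 9.

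The second reading would carry an early score forward to Week 24. Protocol 4.4.2 reports that improvement in Phase 2 was progressive through 24 weeks, so such a score would tend to understate response. It would also count as observed, and so would escape the imputation, the tipping-point shifts and probably the control-based analysis. If two programmers could derive different primary-endpoint data from the same text, that would deserve attention.

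**Working it through.** **1. The plan's own power figure.** Inputs from Protocol 12.1: response 40%, 26% and 9%; 110, 220 and 110 patients; continuity-corrected chi-square; two-sided alpha 0.025 (z = 2.2414). Formula: power = Φ[(d − c − z·SE0)/SE1], with c = 0.5(1/n1 + 1/n2), SE0 from the pooled rate and SE1 from the separate rates.

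- 8 mg: d = 0.17, c = 0.0068, SE0 = 0.0470, SE1 = 0.0402. (0.17 − 0.0068 − 2.2414 × 0.0470)/0.0402 = 1.437, so power is 92.5% (stated: about 92%).
- 12 mg: d = 0.31, c = 0.0091, SE0 = 0.0580, SE1 = 0.0541. The ratio is 3.16, so power is 99.9% (stated: above 99%).

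**2. How much time is uncovered.** The SALT efficacy windows are Days 26-32, 54-60, 82-88, 110-116, 138-144 and 166-172. Days 2-165 are 164 days. Five windows of seven days cover 35 of them, leaving 129, and 129/164 = 78.7%. The gap is real.

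**3. Which reading the text supports.**

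- ET visits are to be mapped by window, and Table 2 is titled for unscheduled and ET visits. If every ET score outside a window defaulted to Week 24, the Days 166-172 limit would not bind on the visits it was written for.
- The reference to the schedule in 8.1.2 is explained in the next sentence as a restriction on reassignment. It is not a fallback to the ET column.
- The schedule dates visits from Day 1 with ±2 days, so a visit months early is not Week 24 there either. The shared column tells sites which procedures to perform.
- Contiguous safety windows stand beside gapped efficacy windows in one table. That suggests the authors chose not to map every efficacy day.
- Sensitivity 1 imputes scores missing after a patient leaves. If the ET score filled Week 24, that analysis would not reach the primary endpoint of the patients it targets.

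**4. Size if the unlikely reading were programmed.** The documents give no ET rate, timing or response curve, so these are assumptions: ET share d = 5-10% in every arm, each with a SALT score; a share s = 0-50% of ET visits on scheduled days and the rest spread evenly; response rising linearly from Week 4 or Week 8 to Week 24. The mean fraction f of the Week 24 rate reached on the gap days is then 0.41 (from Week 4) or 0.33 (from Week 8). With imputation at the planned rate as reference, each response rate shrinks by k = d × (129/164) × (1 − s) × (1 − f).

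- Smallest case (5%, half on schedule, from Week 4): k = 0.05 × 0.787 × 0.5 × 0.593 = 0.0117. 8 mg: 17 × 0.0117 = 0.20 points, power 92.0%. 12 mg: 31 × 0.0117 = 0.36 points.
- Largest case (10%, none on schedule, from Week 8): k = 0.10 × 0.787 × 0.674 = 0.0530. 8 mg: 17 × 0.0530 = 0.90 points, power 90.2%. 12 mg: 31 × 0.0530 = 1.64 points, power still 99.8%.

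The standard errors of the planned differences are 4.0 points (8 mg) and 5.4 points (12 mg), so the largest shift is 1.64/5.4 = 0.3 standard errors. The number of gap-day scores runs from 440 × 0.05 × 0.787 × 0.5 = 9 to 440 × 0.10 × 0.787 = 35. A simulation with within-arm sequential imputation and the stratified Mantel-Haenszel risk difference (300 replicates per case) gave −0.22 to −0.91 points for 8 mg and −0.42 to −1.59 for 12 mg.

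**5. Whether the gapped windows themselves cost anything.** In the same simulation, contiguous windows used only to fill empty visits moved the result under the natural reading by 0.01 to 0.12 points.

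**The case for a change.** The strongest case for a change is that no sentence excludes the second reading. SAP 8.2.1 calls a SALT score missing when its total cannot be calculated, which does not describe a valid score outside every window. The same silence reaches SPRO, which is scheduled only from Week 12. Its windows before Week 24 cover 21 of the 164 days, leaving 143. It also reaches HADS, which has one post-baseline visit and no imputation, so the reading decides whether a leaver enters the ANCOVA. Under harsher assumptions the effect grows: if no gap-day score is a response, 8 mg power is 90.8% at 5% ET, 88.9% at 10% and 84.3% at 20%.

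The textual gap stands, but the inference from it does not. The absence of an explicit exclusion does not make a reading plausible when Table 2, the restriction in 8.1.2, the schedule footnotes and the imputation text all point the other way. The same window logic settles SPRO and HADS. The harsher figures need a high ET rate and no early responders, and they apply only if the less natural reading is programmed. On its plain words the Kaplan-Meier plot counts any post-baseline score, and its p-values are declared descriptive.

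**Conclusion.** This is missing detail that an analyst following the SAP would fill correctly. An ET score in no efficacy window belongs to no visit, Week 24 is imputed, and the earlier scheduled scores still inform the imputation. That is a sound result, and spelling it out would alter no analysis. The affected group is narrow: patients who leave the study and have an off-schedule ET SALT. Those who only stop drug keep their scheduled visits.

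Even the unlikely reading would reduce the apparent benefit and not inflate it: about 0.2-0.9 points for 8 mg and 0.4-1.6 for 12 mg, with 8 mg power of about 90-92% against 92.5%. Those figures rest on the assumed 5-10% ET rate, 0-50% of ET visits on scheduled days and response from Week 4 or 8. An extra run with contiguous windows would gain nothing.

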#### 8.1.3. **Timing of Analyses**

All final, planned analyses will be performed after the last patient has completed all study assessments, all relevant study data have been processed and integrated into the analysis database, and the database has been locked.

Any post hoc, exploratory analyses completed to support planned study analysis, which were not identified in this SAP, will be documented and reported in appendices to the CSR. Any results from these unplanned analyses (post hoc) will also be clearly identified in the text of the CSR.

#### 8.1.4. Multiple Comparisons/Multiplicity

Hierarchical testing will be used to control for multiple comparisons (Figure 1). For the primary efficacy analysis and the key secondary efficacy analyses, a  $\leq 0.025$  (two-sided) alpha-level will be allocated to each dose for comparison with placebo to adjust for multiplicity of testing associated with two doses. Once p>0.025 is observed for a treatment group comparison, inference for additional endpoints is no longer alpha-level protected for that dose group, however nominal p-values will still be reported.

Subsequently, conditional upon significance ( $\leq 0.025$ ) for the primary endpoint and first key secondary endpoint for each dose, a linear hierarchical testing approach with  $\leq 0.025$  (two-sided) alpha-level will be used to test the remaining key secondary endpoint comparisons versus placebo. Once p>0.025 is observed for a treatment group comparison, inference for additional endpoints is no longer alpha-level protected for that dose group; however, nominal p-values will still be reported.

All other statistical tests outside of the hierarchy will be carried out at a two-sided significance level of  $\leq 0.05$ . Nominal p-values will be presented without adjustment for multiple comparisons.

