#### 12. STATISTICAL METHODS

## **12.1.** Sample Size Rationale

Power is calculated for the Primary Efficacy Endpoint for the continuity-corrected chi-square test using a 2-sided significance level of 0.025. Based on Phase 2 results, the percentage of patients achieving an absolute SALT score ≤20 at Week 24 is assumed to be 40%, 26%, and 9% for the CTP-543 12 mg, CTP-543 8 mg BID, and placebo groups, respectively. Patients will be randomized in a 1:2:1 ratio with a total N of approximately 440 patients (i.e., 110 for 12 mg BID, 220 for 8 mg BID, and 110 for placebo BID). These sample sizes will provide >99% power for the comparison of CTP-543 12 mg BID versus placebo and approximately 92% power for the comparison of CTP-543 8 mg BID versus placebo.

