#### 12.4.3. Multiplicity

Hierarchical testing will be used to control for multiple comparisons. For the primary efficacy analysis and the key secondary efficacy analyses, a  $\leq 0.025$  (two-sided) alpha-level will be allocated to each dose for comparison with placebo to adjust for multiplicity of testing associated with two doses. The below figure displays the order of testing of the key secondary endpoints. Once p>0.025 is observed for a treatment group comparison, inference for additional endpoints is no longer alpha-level protected for that dose group, however nominal p-values will still be reported.

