#### **Figure 1: Hierarchical Testing**

#### 8.3.1. Satisfaction of Hair Patient Reported Outcome (SPRO) at Week 24

The first key secondary endpoint is the percentage of responders per the SPRO at Week 24. The SPRO is a single item questionnaire answered by the patient, designed to measure how satisfied alopecia areata patients are with their hair at the time of the assessment. The SPRO responses are on a scale of 1-5, where 1 = very satisfied, 2 = satisfied, 3 = neither satisfied nor dissatisfied, 4 = dissatisfied, and 5 = very dissatisfied. An example of the SPRO assessment can be found in Appendix 17.4.1 of the protocol.

A responder is defined as patients with answers of "very satisfied" or "satisfied" at Week 24 on the SPRO. This endpoint will be assessed similar to the primary analysis of the primary endpoint, according to Section 8.2.2.

Missing data will be imputed similarly to the primary endpoint according to Section 8.2.1. However, since the SPRO scale is ordinal, the FCS logistic regression method will be used in lieu of the FCS regression method. The missing SPRO scores will be imputed in a sequential manner using logistic regression models with baseline SALT score, baseline SPRO score, and the observed or imputed SPRO values of previous visits as covariates.

The observed number and percentage of SPRO responders by treatment group will be reported along with the appropriate p-values. Both CTP-543 doses will be tested in parallel against placebo with a  $\leq 0.025$  alpha level. This analysis will be completed for the Efficacy Population, the Per Protocol Population, and the Modified Efficacy Population. The Per Protocol Population will be considered supportive. The analysis utilizing the Modified Efficacy Population is considered a sensitivity analysis. If the primary endpoint is unsuccessful, nominal p-values will be reported.

#### 8.3.2. SALT Score ≤ 20 at Weeks 20, 16, 12, and 8

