The next key secondary endpoints are the percentage of patients achieving an absolute SALT score of  $\leq 20$  (i.e., the binary endpoint denoting a SALT score  $\leq 20$ ) at Weeks 20, 16, 12, and 8. Missing data will be imputed according to Section 8.2.1. These endpoints will be assessed according to Section 8.2.2. If the primary endpoint and first key secondary endpoint are unsuccessful, nominal p-values for the SALT key secondary endpoints will be reported. This analysis will be completed for the Efficacy Population, the Per Protocol Population, and the Modified Efficacy Population. The Per Protocol Population will be considered supportive. The analysis utilizing the Modified Efficacy Population is considered a sensitivity analysis.

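### Optional improvement: alpha from a dose that wins all six of its tests could pass to the other dose, keeping familywise error at 5% and losing no rejection

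*SAP*

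**What the plan says.** SAP 8.1.4 and Protocol 12.4.3 give each dose 0.025 two-sided: the "alpha-level will be allocated to each dose for comparison with placebo to adjust for multiplicity of testing associated with two doses". Protocol 12.1 powers the study on the same basis, "using a 2-sided significance level of 0.025".

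The order within a dose starts with the primary endpoint. SAP 8.3.1 continues: "The first key secondary endpoint is the percentage of responders per the SPRO at Week 24". SAP 8.3.2 then says: "The next key secondary endpoints are the percentage of patients achieving an absolute SALT score of" ≤20, at Weeks 20, 16, 12 and 8. That makes six hypotheses per dose.

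The stopping rule in Protocol 12.4.3 is: "Once p>0.025 is observed for a treatment group comparison, inference for additional endpoints is no longer alpha-level protected for that dose group". SAP 8.1.4 gives the same rule twice. For SPRO, SAP 8.3.1 adds: "Both CTP-543 doses will be tested in parallel against placebo with a" level of 0.025.

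No sentence says what happens to a dose's 0.025 after all six of its tests succeed. SAP Section 13 lists no change to multiplicity. Figure 1 is not visible in the text available, but the wording around it uses 0.025 at every step.

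**The concern.** When every hypothesis for one dose has been rejected, that dose's 0.025 has done its work. Under the written rule it lapses, and the other dose is still held to 0.025. If one dose is fully effective and the other has no effect, the familywise error is then 2.5% rather than the permitted 5%.

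The comparison with something to gain is 8 mg. It has the smaller assumed effect (26% vs 9%, against 40% vs 9% for 12 mg), while the protocol already puts power for the 12 mg primary above 99%. At stake are label-supporting claims for 8 mg with p-values between 0.025 and 0.05 in a trial where 12 mg has won everything.

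**Working it through.** **Inputs.** From Protocol 12.1: n = 110 (12 mg), 220 (8 mg), 110 (placebo); Week 24 rates 40%, 26%, 9%; continuity-corrected chi-square test; two-sided 0.025. The six-step order is from SAP 8.3.1 and 8.3.2. The Week 8 rates below are assumptions, because the documents give none.

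**1. Reproduce the stated power (8 mg vs placebo).**
- Pooled rate = (220 × 0.26 + 110 × 0.09)/330 = 0.2033.
- SE under the null = √[0.2033 × 0.7967 × (1/220 + 1/110)] = 0.0470.
- SE under the alternative = √(0.26 × 0.74/220 + 0.09 × 0.91/110) = 0.0402.
- Continuity correction = 0.5 × (1/220 + 1/110) = 0.0068.
- Power = Φ[(0.17 − 0.0068 − 2.241 × 0.0470)/0.0402] = Φ(1.437) = 92.5%.

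The protocol states about 92%, so it reproduces. The same formula gives 99.9% for 12 mg, against a stated >99%.

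**2. Ceiling on the 8 mg primary gain.** Passing alpha adds a rejection of the 8 mg primary only when 0.025 < p ≤ 0.05 and the 12 mg chain is complete. The most it can add is the difference in power between the two levels (exact binomial enumeration, 26% vs 9%):

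| Test | at 0.025 | at 0.05 | Ceiling |
|---|---|---|---|
| Continuity-corrected | 92.9% | 96.4% | 3.5 points |
| Uncorrected | 95.1% | 97.5% | 2.4 points |

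The protocol's power statement uses the corrected test. The Mantel-Haenszel risk-difference test in SAP 8.2.2 specifies no correction, so the second row is closer to the planned analysis.

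**3. Familywise error with passing.**
- *Each dose has at least one true null.* A chain cannot complete unless its first true null is rejected. Until one of the two first true nulls is rejected, no alpha passes and both are tested at 0.025. Any error therefore needs one of two p-values ≤0.025, with probability at most 0.025 + 0.025 = 0.05.
- *All nulls for one dose are false.* Errors can arise only in the other dose. They need its first true null to have p ≤0.05, with probability at most 0.05.

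This holds under any correlation, including the shared placebo arm. A simulation (200,000 runs per setting; correlation between doses 0 or 0.577, between adjacent endpoints 0 or 0.7) agrees. With one dose fully effective and the other null, the error is about 0.025 under the current rule and about 0.050 with passing. In the other settings the two rules give the same value, 0.045 to 0.050. The highest single value with passing was 0.0511, in a setting where the error is exactly 0.05 by construction, so the excess is simulation noise.

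**4. No rejection is lost.** Every test keeps its place in the order and is made at 0.025 or higher. In the simulated power runs, passing never removed a rejection for either dose.

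**5. How often the gain is available.** The 12 mg chain cannot complete more often than its Week 8 test succeeds. Exact power of that test at 0.025, 110 vs 110:

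| Assumed Week 8 rates, 12 mg vs placebo | Uncorrected | Corrected |
|---|---|---|
| 3% vs 1% | 8.5% | 1.8% |
| 7% vs 1% | 53.8% | 38.5% |
| 10% vs 0.5% | 91.2% | 83.9% |

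Simulated 8 mg primary power (corrected baseline 92.5%) by probability that the 12 mg chain completes:

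| 12 mg chain complete | 10% | 30% | 50% | 70% | 88% | 98% |
|---|---|---|---|---|---|---|
| 8 mg primary power | 92.8% | 93.3% | 93.9% | 94.5% | 95.2% | 95.6% |

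Later 8 mg steps could gain more. As an illustration with assumed effects, an 8 mg chain that reaches and wins Week 12 with 44% probability rises to about 56% when the 12 mg chain completes 98% of the time.

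**The case against.** The current rule is valid and prespecified, and 8 mg is already powered at about 92% with twice the patients of the other arms. Nothing is broken. That stands, and it is why the point is optional.

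A reader might infer that the change raises 8 mg power as a matter of course. The documents do not support that. The gain needs 12 mg to win at Week 8, and the only timing evidence is in Protocol 4.4.2, where Phase 2 separation is reported from Week 12. The most favourable scenario above assumes 10% vs 0.5%, which is about half a placebo responder in 110.

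A reader might also infer that the early-week 8 mg tests are badly underpowered. No 8 mg rates for Weeks 8 to 20 are given, so this cannot be shown.

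Figure 1 is not visible, and SAP 8.1.4 describes the later steps somewhat loosely. A passing rule in the figure cannot be excluded outright, but it would contradict the fixed threshold in the text.

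Finally, one added sentence alone would clash with other text that fixes 0.025, including the tipping-point trigger. That is correct, and the fix below covers it.

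**Conclusion.** The point holds as an optional improvement that costs no power on any test. The plan controls familywise error at 5%, but as written it leaves half of that unused when one dose's hypotheses are all false and its chain is fully rejected. Passing that alpha on is valid under any correlation and rejects everything the current rule rejects, sometimes more.

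The size is modest and conditional: at most 3.5 points (corrected) or 2.4 points (uncorrected) on the 8 mg primary at 26% vs 9%, and close to nothing if 12 mg rarely wins at Week 8. In the other direction, from 8 mg to 12 mg, the 12 mg primary has almost nothing to gain.

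The power figures assume complete data and unstratified two-proportion tests. The stratified analysis with multiple imputation was not simulated. The error-control argument needs only that each individual test holds its level.

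**What to change.** Before unblinding:

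1. Add to SAP 8.1.4 and Figure 1: *If all six hypotheses for one dose are rejected at 0.025, its alpha passes to the other dose, whose sequence is then tested from its first hypothesis at 0.05.* Keep the order and the starting split.
2. In the stopping sentences of SAP 8.1.4 and Protocol 12.4.3, replace the fixed 0.025 with the level currently assigned to that dose. SAP Section 2 gives the SAP primacy where the two differ.
3. Make the same replacement for the SPRO test in SAP 8.3.1.
4. Tie the tipping-point trigger in SAP 8.2.3 (Sensitivity 2) to that level too. Otherwise an 8 mg primary result won only at 0.05 would get no tipping-point analysis.
5. State that Week 8 ends the chain. Protocol 12.2.1 lists SALT ≤20 at Week 8 both as a key secondary and as an ordinary secondary endpoint.
6. Record the change in SAP Section 13.

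The cost is wording edits and a revised figure. There are no added patients or assessments, and no test loses power.
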